Phase 1 and Phase 2 measures will be used to achieve **2 Specific Aims**:

Aim 1. *To assess the acute effects of MEM (0 vs. 20 mg) on measures of early auditory information processing (EAIP) in patients with mild-to-moderate severity AD.* Measures of PPI, MMN and ASSR will be assessed in 88 individuals with mild-to-moderate severity AD after placebo (PBO) and 20 mg MEM po, in a double-blind, randomized order cross-over design. **Hypothesis 1:** Assessed across the full cohort of patients, PPI, MMN and ASSR will be significantly greater after MEM vs. PBO. However, the response to MEM will be heterogeneous: the magnitude of this “MEM effect” (MEM minus PBO) will vary across the dependent measures, and across patients, with some patients demonstrating robust increases in EAIP measures after MEM, and other demonstrating little response or reduced EAIP performance.

Aim 2. *To determine the ability of MEM-induced alterations in EAIP in AD patients to predict their clinical response to MEM.* The magnitude of the “MEM effect” will be calculated for each patient and each EAIP measure. MEM treatment will be initiated and titrated to 10 mg bid in all patients. Clinical severity will be assessed at baseline, 8, 16 and 24 weeks using the ADAS-cog as a primary measure. Analyses will determine whether the MEM effect on some or all EAIP measures moderates the magnitude of the clinical response to MEM. **Hypothesis 2:** Patients exhibiting a larger “MEM effect” on EAIP measures will exhibit a more robust positive clinical response to MEM, compared to patients exhibiting a smaller MEM effect on EAIP measures. This hypothesis will be tested empirically for each of the primary EAIP measures, and for regression-derived composite scores from multiple EAIP measures.

Analyses (linear mixed-effects model) will test the hypothesis (H2) that EAIP MEM sensitivity (in Phase 1) predicts the clinical response to MEM (in Phase 2). Moderating roles of specific variables on MEM sensitivity will be assessed, including demographic/clinical variables, baseline neuropsychological measures and genotypes associated with MEM sensitivity or AD. Source localization will identify anatomical substrates associated with MEM effects on EAIPs, and enable us to test structure- and circuit-based mediation models.

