Specifically, we hypothesize and will test in Aims 1-2 that in AD patients, evidence of MEM-enhanced EAIP will predict a superior clinical response to MEM. Prior to starting a standardized MEM treatment regimen, subjects not currently receiving AD medications will be tested to their EAIP response to placebo or a single pill of MEM (20 mg). They will then be followed clinically during MEM monotherapy, consisting of a titration to a daily dose of 10 mg bid for 24 weeks. Clinical indices will be assessed at baseline, weeks 8, 16 and 24. Clinical responses will then be compared across groups stratified by the magnitude of MEM-enhanced EAIP (Fig. 3), and the relationships of MEM-enhanced EAIP measures to the magnitude of clinical gains will be tested using both discrete (ANOVA) and continuous (linear mixed-effects model) approaches. Secondary analyses will be used to optimize criteria for EAIP "MEM sensitivity", to determine whether EAIP MEM sensitivity also predicts the rapidity and durability (in addition to the magnitude) of MEM's clinical benefits, and whether specific demographic, clinical and genetic factors moderate the predictive strength of MEM EAIP sensitivity. If our hypothesis is supported by these findings, we plan to expand our tests in future applications to include combination therapies (MEM+AChE-I) vs. AChE-I monotherapy, and MCI / early AD patients, with the prediction that combined regimens (but not AChE-I monotherapy) will also produce superior gains among subgroups exhibiting the greatest MEM-enhanced EAIP response. Positive findings in this application may also justify tests with other AD therapeutics for which an acute EAIP-based laboratory biomarker is available.

Summary: Current therapeutics for AD are suboptimal. In particular, clinical response to MEM in AD is variable and modest. One strategy to enhance treatment efficacy is to prospectively identify "drug-sensitive" subgroups, based on the presence of predictive biomarkers for drug response (Fig. 1). MEM enhances neurophysiological measures of EAIP in healthy subjects as well as patients with SZ (Fig. 2). We now propose to determine if greater sensitivity to MEM-enhanced EAIP (Fig. 3) predicts a superior therapeutic impact of MEM in AD patients. This application is thus responsive to **PAR-16-365**, and its specific calls for "**Studies to define and refine the target population...**" and "**Studies that address heterogeneity of response.**"

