Design Overview: The general study design is modeled after that employed by Peskind et al. (79) and Pomara et al. (81). These authors conducted a 24-week, multi-site placebo-controlled randomized trial of MEM monotherapy (10 mg bid) in mild-to-moderate AD, demonstrating significant gains in cognitive, global and behavioral measures. The present study will differ from that of Peskind et al. (79) in 3 major ways: 1. Patients will be characterized at baseline to assess their EAIP response to a MEM “challenge dose” (20 mg); 2. This is a single site study; 3. All patients will receive MEM treatment; to test the key hypothesis (H2), analyses will compare groups stratified by the magnitude of their EAIP response to MEM. Other minor methodological differences will be described below.

88 AD patients who consent to participation undergo a full neurocognitive characterization and medical evaluation. Patients also receive baseline ADAS-cog assessment and secondary outcome measures (described below) by [name] (Neuropsychologist; Clinic Director: UCSD Memory, Aging and Resilience Clinic [MARC]; Co-I).

Patients will then be tested in a PBO-controlled double-blind within-subject cross-over study of the effects of 20 mg MEM po on EAIP measures (PPI, MMN, ASSR). This proposed “N” is adequate to be stratified into “low” vs. “high” MEM sensitivity using discrete criteria, eg. median split, for categorical analyses (eg. ANOVA) and to detect medium effect size ($d=0.5$) differences in outcome between MEM-sensitive vs. -insensitive patients (see “Power Considerations”). Inclusion and exclusion criteria are seen in Table 2.

Table 1. Inclusion and exclusion criteria

Inclusion: 1. ADRC-confirmed diagnosis of AD; 2. **MMSE score 10-22**; 3. Age 50-70 y; 4. Knowledgeable caregiver; 5. Ambulatory; 6. Medically stable; 7. Audiometric testing (detection ≤ 40 db(A) at 1000 Hz); 8. Informed consent.

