Aim 1: Repeated measure (Rm)-ANOVAs will determine whether PPI, MMN and ASSR significantly differ after MEM vs. PBO (Hypothesis 1). Primary variables for each EAIP, as well as exploratory "secondary" measures, are identified above. Based on a recruited sample of 88 total participants, we will have 80% power to detect effect sizes of $d = 0.35$ (small) using a Bonferroni corrected $\alpha = .05/3$ (2-tail). Heterogeneity of response will be characterized using variance components expressed as intraclass correlation coefficients (ICCs).

Aim 2: Linear mixed-effects models regressing change in ADAS-cog outcome scores (at 8, 16, and 24 weeks vs. baseline) onto a fixed effect of group defined by MEM sensitivity will test the hypothesis that patients exhibiting a larger "MEM effect" on EAIP measures will exhibit a larger positive clinical response to MEM. Groups will be defined by a median split of "MEM effect" (MEM minus PBO) on EAIP. Power was estimated using methods described by Hedeker et al. (25) solving for sample size with $\alpha = .05$ (2-tail), test-retest correlations of .50, and 5% attrition at each time point. A sample of 88 total participants provides us with 80% power to detect a medium effect of $d = 0.50$. The primary outcome will be chosen based on effect sizes obtained as part of Aim 1. In exploratory analyses, we will also examine group by time interactions using orthogonal polynomial contrasts. We will also predict change in clinical outcomes as a function of all four candidate biomarkers in order to create an optimal prediction equation. We will perform ROC curve analyses using EAIP MEM sensitivity values as continuous variables and predict clinical improvement after MEM as a discrete outcome (responders vs. non-responders) in order to determine the clinical utility of this approach defined in terms of sensitivity and specificity. Secondary analyses will also be conducted with biomarker groups defined as "MEM-sensitive vs. -insensitive" via specific thresholds for EAIP MEM sensitivity.

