Multiple analytic strategies: The critical test of H2 will utilize both continuous and discrete analyses. Treating EAIP MEM sensitivity as a **continuous variable** will enable us to identify moderating factors (i.e. factors moderating the relationship between EAIP MEM sensitivity and clinical MEM sensitivity) with greater power. By identifying these moderators, and their relative contributions to the biomarker-clinical response relationship, *this continuous approach will potentially be more informative regarding the mechanisms by which EAIP MEM sensitivity is related to MEM's clinical impact*. Compared to ANOVA, a linear mixed-effects model is also relatively less impacted by missing data.

Treating MEM sensitivity as a **discrete variable** will enable us to divide the patient sample via a specific threshold, eg. median split, based on EAIP MEM sensitivity (Fig. 3). Exploratory analyses will test more or less stringent thresholds, aiming to optimize the positive and negative predictive value of this discrete threshold. *This approach has the potential practical value of establishing preliminary criteria for distinct MEM-sensitive and MEM-insensitive clinical subgroups.*

Secondary / Exploratory Analyses: To test H2, we will examine multiple metrics of **EAIP MEM sensitivity**:

1. **primary** measures from each individual EAIP measure (described above);
2. **secondary** composite variable based on these 4 primary measures, generated via multiple regression;
3. **exploratory** measures of EAIP: P3a amplitude and RON (described above).

An underlying premise of H2 is that the neurobiological bases of MEM effects on the Aim 1 EAIP measures share some amount of variance, and hence positive and negative predictive value, with the clinical therapeutic response to MEM in AD. However, MEM effects on these 4 EAIP primary measures likely reflects its actions on (overlapping but) non-identical neural substrates; this is consistent with findings that MEM sensitivities on these measures are positively correlated for some (MEM effects on MMN and ASSR (65)) but not other measures (MEM effects on PPI and MMN (99)). *Which of these primary measures, or composite measure, provides the best prediction of MEM effects on AD-relevant neural substrates, and hence provides the best prediction of MEM's therapeutic sensitivity, is an important empirical question that we will address in Aim 2.*

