taking an AChE-I; this would significantly complicate interpreting a negative finding in Aim 1. In fact, studies in laboratory animals and HS report complex and drug-dependent effects of AChE-I on each of the Aim 1 EAIP measures (27-9,42); 2. MEM added to an AChE-I in mild-to-moderate severity AD has failed to produce clinical gains (82); without evidence of positive therapeutic impact in the absence of biomarker stratification, it will be difficult to interpret a negative findings in the present study; 3. The mechanistic interpretation of any positive findings in the present study will be much more complex if patients are using a combination regimen. Nonetheless, we recognize that patients may opt to add an AChE-I to their MEM regimen in the course of this study. If this occurs, and patients also remain adherent to MEM, outcome measures will be collected analyzed with a grouping structure that distinguishes them from patients who remain on MEM monotherapy.

Parenthetically, MEM significantly enhanced EAIP measures in SZ patients, despite their use of complex medication regimens, including antipsychotics, antihypertensives and anticholinergics (99). This suggests that complex medication regimens in AD patients should not obscure the primary “biomarker”, with the possible exception of AChE-I’s, which are thus an exclusion criterion.

Why 24 weeks of treatment? In several studies, MEM benefits vs. placebo in mild, moderate and severe AD first become evident by week 8; by week 24, clinical symptoms in MEM-treated patients have typically returned to pre-MEM baseline, though their progression is effectively delayed by 24 months, compared to placebo-group patients (eg. 81). Thus, while our primary analyses will assess whether the clinical response to MEM is **larger** in EAIP-defined “MEM sensitive” vs. “MEM-insensitive” patients, a 24-week study should also enable us pursue secondary analyses to determine whether “MEM-sensitive” individuals experience clinical gains from MEM that are **more rapid** or **more durable**, compared to “MEM-insensitive” individuals.

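### The plan does not say whether the median split or the continuous analysis decides H2, and the H2 model leaves out baseline ADAS-cog

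*Combined protocol and SAP*

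**What the plan says.** All references are to the combined protocol and SAP.

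- **Statistical tests for each hypothesis, Aim 2.** A mixed model regresses ADAS-cog change at weeks 8, 16 and 24 "onto a fixed effect of group defined by MEM sensitivity will test the hypothesis". On the predictor: "Groups will be defined by a median split of" the MEM effect. The power statement (88 patients, d = 0.50, two-sided .05, correlation .50, 5% attrition per time point) belongs to this comparison.
- **Same paragraph.** "The primary outcome will be chosen based on effect sizes obtained as part of Aim 1". ADAS-cog is already fixed as the primary clinical outcome elsewhere, so this may mean the deciding EAIP measure. The text does not say so.
- **Design Overview.** For H2, "analyses will compare groups stratified by the magnitude of their EAIP response to MEM". The section Why 24 weeks of treatment? also frames the primary analyses as sensitive against insensitive patients.
- **Multiple analytic strategies.** "The critical test of H2 will utilize both continuous and discrete analyses". The Innovation section likewise plans to relate EAIP change to clinical gain "using both discrete (ANOVA) and continuous (linear mixed-effects model) approaches".
- **Specific Aims, Aim 2.** "This hypothesis will be tested empirically for each of the primary EAIP measures". The Secondary / Exploratory Analyses section counts four such measures.
- **Covariates.** Sex is planned as a factor in all major analyses. Baseline outcome scores appear only among the moderators to be explored.

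**The concern.** Two things are open.

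**Precedence.** One section gives the split model as the test of H2; another calls both forms the critical test. The model's name does not settle it: the Innovation section uses linear mixed-effects model for the continuous approach, while the Aim 2 section applies it to the split. If the two forms disagree, the plan does not say whether H2 is supported. It also does not say which of the four EAIP measures carries the test, and Aim 2 is powered at an undivided .05.

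**Efficiency.** A median split discards the ordering within each half. The outcome is change from baseline, but subtracting baseline is not the same as adjusting for it. Baseline ADAS-cog is collected in every patient, so leaving it out of the model gives up precision in a single-site study of 88.

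**Working it through.** **1. The plan's own figure.** Inputs from the Aim 2 section: α = .05 two-sided, power .80, d = 0.50, three follow-up visits, correlation .50, 5% lost at each time point.

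n per group = 2(1.960 + 0.842)² / (d² × I), where I is the information per patient on the time-averaged difference.

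- No attrition: I = 3/(1 + 2 × .5) = 1.5. n = 15.70/(0.25 × 1.5) = 41.9 per group, 84 in total. Power at 44 per group is 0.819.
- Retention 1, .95, .9025 with equal visit weights: I = 1.424, n = 44.09 per group, power 0.799.
- Same retention, generalised least squares: 42.8 per group, power 0.811.
- Loss already present by week 8: power 0.78-0.79.

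The stated 88 and 80% reproduce.

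**2. What the split keeps.** For a normal MEM effect and a linear relation, the efficiency is corr(X, split)² = 2/π = 0.637, about 64%. For other predictor shapes, still with a linear relation, it is 75% (uniform), 54% (t with 5 df) or 50% (Laplace). The distribution figure is not available to check the shape.

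**3. What baseline adds.** Assume compound symmetry with correlation ρ across baseline and the three follow-ups.

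- Variance of mean change: 4(1 − ρ)/3.
- Variance of mean follow-up adjusted for baseline: (1 + 2ρ)/3 − ρ².
- Ratio: (1 + 3ρ)/4 = 0.625 at ρ = .5, 0.85 at .8, 0.925 at .9.

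Under this structure two change scores correlate .5 whatever ρ is, so unadjusted power does not depend on ρ. The plan's .50 is not stated to be a baseline-to-follow-up correlation, so ρ is an assumption.

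**4. Simulated power.** n = 88, three visits, complete data, sex in the model, two-sided .05, gap between halves 0.5 SD of one change score. Artefact means that 5% of patients carry noise of 5 SD in the predictor (assumption).

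| True relation | Planned split | Split + baseline (ρ .5 / .8) | Raw slope + baseline (ρ .5 / .8) | Normal-score slope + baseline (ρ .5 to .9) |
|---|---|---|---|---|
| Linear | 0.78 | 0.92 / 0.83 | 0.99 / 0.96 | 0.99 to 0.94 |
| Linear, 5% artefact | 0.74 | 0.90 / 0.80 | 0.80 / 0.71 | 0.96 to 0.87 |
| Step at sample median | 0.81 | 0.95 / 0.86 | 0.79 / 0.66 | 0.80 to 0.63 |
| Step at population median | 0.73 | 0.89 / 0.79 | 0.79 / 0.66 | 0.79 to 0.62 |

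Split plus baseline at ρ = .9, linear, is 0.80. Repeat runs agree to about one point. The planned split is at 0.78 rather than 0.82 mainly because a linear relation leaves some of its own spread inside each half.

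**5. Why precedence matters.** In the linear case at the 0.5 SD gap, the unadjusted split and unadjusted raw slope disagree in about 17-18% of trials. Under the null each rejects in about 5%, and at least one rejects in about 8%.

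**The case against.** **The documents describe a subgroup.** The sections Why Mild-to-Moderate AD? and Why test only 20 mg MEM vs. EAIP? speak of a nested sensitive subgroup and of a threshold, and Multiple analytic strategies gives a practical reason for a cut-point. A split fits that question, and the table shows it winning when there is a step at the median. This stands. It is why the gain from a slope is conditional, and why the split should stay as a named secondary test.

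**The Aim 2 section already makes the split primary.** Its position and its power statement favour that reading. The critical-test sentence then conflicts with it, and one sentence is still needed.

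**Baseline is already in the change score, and the groups are not randomised.** Change scores do not recover the precision in step 3, but the second half has force. A stable 0.2 SD baseline gap with no true difference in change shifts the adjusted contrast by 0.2(1 − ρ): 0.10 SD at ρ = .5, 0.04 at .8. A chance gap of that size shifts the unadjusted contrast equally. Both models should therefore be reported.

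**Stronger readings that the documents do not support.**
- A reader might infer that the trial is underpowered. Step 1 shows that it is not.
- A reader might infer that the continuous analysis is missing. It is planned, but not ranked.
- A reader might infer inflated error. With both forms and four measures at .05, some p < .05 occurs in 23-28% of null trials (correlation between measures .6 to 0), against 14-19% for four continuous tests alone. No passage says that any one such result establishes H2, so these figures are only a reason to fix precedence.

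**Conclusion.** The concern holds as one of precedence and efficiency. No passage ranks the two forms of the H2 test, and the specified model omits a baseline score that is already collected.

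The firmer part is the covariate: adding baseline raised power for every predictor form in every scenario run. For the split in the linear case the gain is about 15 points at ρ = .5, 6 at .8 and 3 at .9.

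The choice of predictor is less certain. A reader might take 0.78 against 0.96-0.99 as the general gain from a raw continuous slope. That contrast needs a linear relation and a clean, roughly normal predictor. At ρ = .8 the raw slope with baseline falls below the plan's own unadjusted split under a step at the sample median (0.66 against about 0.80) or 5% artefact (about 0.70 against 0.74). Normal scores remove the artefact problem at a cost of under one point with clean data, but not the step problem. The 64% figure is likewise conditional, with about 50-75% over the other shapes tried.

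**What to change.** 1. Add baseline ADAS-cog, alongside sex, as a covariate in the H2 mixed model whichever predictor form is used. Report the model without it as a sensitivity analysis.
2. Before Aim 2 outcomes are analysed, add one sentence naming the single deciding H2 test and the EAIP measure it applies to, or else control multiplicity across the four primary measures. Say whether the primary outcome to be chosen from Aim 1 effect sizes means that measure.
3. Preferred deciding test: the slope of ADAS-cog change on the rank-based normal score of the MEM effect. Keep the baseline-adjusted median split as the secondary test that supplies the subgroup criteria.
4. State the downside: under a step at the median the preferred test has about 0.63-0.80 power against 0.81 for the planned split (sample median), or 0.62-0.79 against 0.73 (population median). If the team regards a step as the more plausible shape, the baseline-adjusted split can be named as deciding instead, provided the choice is made in advance.

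The cost is SAP wording and one model degree of freedom. No new patients, visits or data are needed.
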